9.3.1 Overall Summary of AEs

An overall summary of AEs will be presented and will reflect a count of TEAEs, TEAEs by CTCAE grade, TEAEs by relationship to investigational product, and treatment-emergent serious adverse events (SAEs). Additionally, the table will reflect the count and percentage of subjects experiencing the following: any TEAEs, SAEs, TEAEs classified by relationship to investigational product, and TEAEs by CTCAE grade. All percentages will use the number of subjects in the Safety Set as the denominator.

9.3.2 Subject-level and Event-level Summary of AEs

A summary table will be presented to reflect a count and percentage of subjects experiencing at least 1 TEAE in each system organ class and preferred term and a count of TEAEs occurring in subjects in the Safety Set within each system organ class and preferred term. All percentages will use the number of subjects in the Safety Set as the denominator. A subject

Page 22 of 38

will be counted only once for a category. For the event-level summaries, subjects experiencing more than 1 AE within a category be counted more than once. Tabular summaries will be sorted by descending frequency in subject counts by system organ class and preferred term.

TEAEs and SAEs will also be tabulated by CTCAE grade, relationship to AT-01 administration, and relationship to KI. Each subject will be counted only once within a SOC or PT by using the AE with the highest severity or greatest relationship within each category.

Records with missing CTCAE grade will be counted as severe.

Records with missing relationship to AT-01 or KI will be counted as related.

Listings for all reported adverse events will be provided.

9.4 Deaths, Serious Adverse Events, and Other Significant Adverse Events

Treatment-emergent SAEs, TEAEs leading to study withdrawal, and TEAEs resulting in death will be summarized separately for all subjects in the Safety Set. All percentages will use the number of subjects in the Safety Set as the denominator. Summary tables will reflect a count and percentage of subjects experiencing at least 1 TEAE in each system organ class and preferred term within each AE subset (serious, leading to study withdrawal, leading to death). The tabular summary will be sorted by descending frequency of system organ class and preferred term based on the overall incidence.

Records with missing SAE flags will be counted as SAEs.

Separate listing for SAEs, AEs leading to premature withdrawal from the study, and all deaths will be generated.

9.4.1 TEAEs on Day of Dosing

Infusion-related reactions (IRRs) can be any signs or symptoms experienced by subjects during the infusion of pharmacologic or biologic agents or any event occurring on the first day of the infusion. Treatment-emergent adverse events starting on the day of dosing at each dosing visit will be summarized by SOC and PT in order to evaluate potential IRRs.

A data listing of TEAEs starting on the day of dosing at each dosing visit will be provided.

IRRs which occur during administration will be captured on the AT01 Infusion CRF as any non-blank answer for "If discontinued, provide reason" or "If interrupted, reason for interruption" and will be provided in a listing.

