- d. Subjects must remain semi-recumbent for at least 5 minutes prior to blood pressure measurements. Blood pressure and heart rate will be measured within an hour prior to dosing and 5-10 minutes after administration of ¹²⁴I-AT-01.
- e. Serum pregnancy test, as indicated in Section 10.2, will be obtained in all women of childbearing potential.
- f. Serum pregnancy and all other laboratory samples must be drawn within 7 days prior to administration of ¹²⁴I-AT-01 in all WOCBP. The results of the pregnancy test must be available and be negative prior to ¹²⁴I-AT-01 administration in all WOCBP.
- g. Adverse events will be monitored from Screening through the EOS Visit. For Safety Follow-up 1 and 2, adverse events and concomitant medications can be obtained by phone call.
- h. Clinical laboratory tests and biomarker analysis, as described in Section 10.2. Baseline sample will be collected within 30 days prior to the first administration of ¹²⁴I-AT-01; second sample within 7 days prior to the second administration of ¹²⁴I-AT-01; third sample at Safety Follow-up 1 after the second administration of ¹²⁴I-AT-01.
- i. Urine and blood may be collected locally by visiting nurse/phlebotomist. An additional serum ADA sample will be obtained at Screening for subjects who provided consent for the extra ADA sample.
- j. Safety follow-ups for concomitant medications and adverse events will be done via telephone call for all subjects. Both Safety Follow-up 1 and Safety Follow-up 2 activities will be conducted for subjects who discontinue for IRRs at either the first or second administration of ¹²⁴I-AT-01.
- k. Blood draw for ADA should be obtained if ET is ≥4 weeks after first administration of ¹²⁴I-AT-01.
- l. Early Termination activities do not apply to subjects discontinued for IRRs. Please follow Safety Follow-up 1 and Safety Follow-up 2 activities for subjects experiencing IRR with either the first or second administration of ¹²⁴I-AT-01.

- 15 -

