4.1.2 Pre-Administration Period

Subjects will begin therapy with KI 130 mg (e.g., iOSAT, Potassium Iodide Oral Solution USP, 65 mg/mL) orally once every day for 3 days beginning at least 30 minutes and within 24 hours prior to dosing with ¹²⁴I-AT-01 on the Day 1 and Week 6 visits to block radioactive iodine uptake in the thyroid gland.

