9.5.4 Safety Analysis

Safety will be assessed through reported adverse events (graded using NCI CTCAE version 5) and changes in laboratory parameters.

Adverse Events

All adverse events occurring during the study will be recorded and classified based on Medical Dictionary for Regulatory Activities (MedDRA) terminology. Only treatment-emergent adverse events (TEAEs), which are adverse events that occur after the start of study drug, will be summarized.

The number and percentage of subjects experiencing TEAEs and SAEs will be tabulated for the safety population by system organ class (SOC) and preferred term (PT). TEAEs and SAEs will be tabulated by severity and relationship to study medication. Each subject will be counted only once within a SOC or a PT by using the AE with the highest severity or greatest relationship, respectively, within each category.

TEAEs or SAEs leading to early discontinuation will be summarized as described above. Treatment-emergent adverse events starting on the day of dosing at each dosing visit will be summarized by SOC and PT to evaluate potential infusion-related reactions.

Listings for all reported adverse events, including SAEs, will be provided. In addition, separate listing for SAEs, AEs leading to premature withdrawal from the study, and all deaths will be generated.

Vital signs will include blood pressure (mmHg) and heart rate (beats per minute). Vital signs will be summarized at Baseline and for each study visit when vital signs were obtained. Changes from Baseline in vital sign measurements will also be summarized. Baseline is defined as the last vital signs obtained prior to the initiation of study drug.

Clinical Laboratory Analyses

Baseline for clinical chemistry parameters is defined as the most recent laboratory measurement obtained prior to the initiation of study drug. Clinical laboratory parameters from the tests itemized in Section 10.2, will be summarized as both absolute value and change from Baseline for each visit per the SoA (Section 1.3).

Laboratory parameters with quantitative abnormalities will be listed as 'flagged' based on the Sponsor's internal guidelines. Flagged laboratory parameters will be presented by incidence and frequency.

Clinical safety laboratory tests performed during the study will be analyzed by a central clinical laboratory.

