9.3 Adverse Events

Adverse events will be coded using the Medical Dictionary for Regulatory Activities (MedDRA) Version 24.1 to identify the system organ class and preferred term. All AEs and SAEs will be recorded from the time of informed consent until the final EOS telephone follow-up (~Week 10).

Treatment-emergent AEs are defined as events that are newly reported or reported to worsen in severity after the start of treatment. Adverse events that occur after the treatment start date, occur on the treatment start date with a time that is equal to or after treatment start time, or that have a missing AE start date will be categorized as treatment-emergent. Treatment-emergent AEs will be summarized for the Safety Set.

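### The day-of-dosing table can count events that began before the second injection as potential infusion reactions, while timed events that began before the first injection are left out

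*SAP*

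**What the plan says.** SAP 9.4.1 defines the table by day and visit: "Treatment-emergent adverse events starting on the day of dosing at each dosing visit will be summarized by SOC and PT". Protocol 9.5.4 plans the same summary. Both give its purpose as evaluating potential infusion-related reactions, and the SAP's description of such a reaction extends to "any event occurring on the first day of the infusion". Neither text sets a clock-time condition against the injection given at that visit.

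Whether an event is treatment-emergent is decided in SAP 9.3. One clause admits "Adverse events that occur after the treatment start date", whatever the hour. Another admits events that "occur on the treatment start date with a time that is equal to or after treatment start time". A third admits events with no start date. The protocol also sets a single anchor, defining these as "adverse events that occur after the start of study drug". Neither document resets the anchor at the second dose.

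Events before an injection will be on record. The Schedule of Activities states: "Adverse events will be monitored from Screening through the EOS Visit". It also marks adverse-event collection in the pre-administration column at both dosing visits.

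**The concern.** The secondary objective is the safety of repeat doses, and Tables 14.3.2.1 and 14.3.2.2 are laid out by visit. A reader will naturally compare the first injection with the second. A higher Visit 2 figure could be taken as a sign of sensitisation when part of it comes from the selection rule. An event that began before an injection cannot be a reaction to that injection.

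Such events are plausible. Potassium iodide is started at each dosing visit "beginning at least 30 minutes and within 24 hours prior to dosing", so its first dose can fall on the morning of the injection. SAP 9.3.2 tabulates events by relationship to potassium iodide, so the plan already treats it as a possible cause.

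**Working it through.** **1. The rule applied at each visit.** The plan states no figure for this table, so there is none to reproduce. Take an event that starts at 07:00 before a 10:00 injection.

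| | Day 1 | Visit 2 date |
|---|---|---|
| SAP 9.3 clause that applies | Treatment start date: time must be at or after the first injection | Later than treatment start date: any time |
| Treatment-emergent? | No | Yes |
| In the SAP 9.4.1 table? | No | Yes |
| Same event, start time missing | Meets none of the three timing clauses | Treatment-emergent, so in the table |

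One exception on Day 1: SAP 9.3 also treats an event as emergent if it is reported to worsen in severity after treatment starts, so a pre-injection event that later worsens may still enter.

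**2. Hours of the dosing date that count.** Let the injection be at clock hour h (assumed; the documents give no dosing time). Timed events are eligible for 24 − h hours on Day 1 and for 24 hours at Visit 2. The ratio is 24/(24 − h):
- h = 8: 24/16 = 1.50
- h = 10: 24/14 = 1.71
- h = 12: 24/12 = 2.00

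If onsets unrelated to the drug were spread evenly over the day, they would be counted 1.5 to 2 times as often at Visit 2.

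**3. Subjects affected.** Let p be the chance that a subject has an event starting on the Visit 2 date before the injection (assumed), with n = 20, the upper figure in SAP 3.3. The expected number is np, and the chance of at least one is 1 − (1 − p)^n.

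| p | Expected subjects | Chance of at least one |
|---|---|---|
| 0 | 0 | 0% |
| 1% | 0.2 | 18% |
| 2% | 0.4 | 33% |
| 5% | 1.0 | 64% |
| 10% | 2.0 | 88% |

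These are upper limits for the any-event line, because a subject who also has a post-injection event that day is already counted.

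**4. The percentage.** SAP 9.4.1 states no denominator. The neighbouring adverse-event tables use the Safety Set, which includes subjects never given a second dose. Let r = 10% be the true post-injection rate at both visits (assumed, and independent of pre-injection events), with n₂ of N = 20 subjects re-dosed. The Visit 2 figure is [1 − (1 − r)(1 − p)] × n₂/N. For example, with p = 2% and n₂ = 16: (1 − 0.90 × 0.98) × 16/20 = 0.118 × 0.8 = 9.4%. Visit 1 shows 10.0% throughout.

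| p | Safety Set, 16 of 20 re-dosed | Safety Set, 18 of 20 re-dosed | Subjects dosed at Visit 2 |
|---|---|---|---|
| 0 | 8.0% | 9.0% | 10.0% |
| 1% | 8.7% | 9.8% | 10.9% |
| 2% | 9.4% | 10.6% | 11.8% |
| 5% | 11.6% | 13.1% | 14.5% |

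The count can move only upward, but a Safety Set percentage can fall on either side of Visit 1.

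**The case against.** The strongest reply is that the table is a deliberately broad screen. The description of an infusion-related reaction covers the whole day, the entries are called potential reactions, and nothing is adjudicated. That would support a whole-day rule at both visits, but the plan does not have one: the SAP 9.3 filter already removes timed pre-injection events on Day 1. Either convention could be defended if used twice. The mixture cannot.

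A second reply is that other displays limit the damage. Interruptions and discontinuations during administration are listed from the infusion case report form (Listing 16.2.7.3). There is a hypersensitivity table by visit (14.3.2.4), and there are separate relationship tables for AT-01 and potassium iodide. Listing 16.2.7.2 can be read case by case in a study of this size. This stands as a limit on the risk of misreading, but none of these displays corrects the table. Nor does SAP 9.4.2: its two periods lie before and after the Visit 2 date, so events on that date fall in neither.

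A third reply is that the table is descriptive, in an uncontrolled study with no hypothesis. That is also true. The primary endpoint is not touched, and the selection rule in SAP 9.4.1 does not alter overall treatment-emergent incidence.

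Some stronger readings go further than the documents allow:
- A reader might infer that second-dose reactions are bound to be inflated. The rule permits extra counts and produces none unless a pre-injection event occurs.
- A reader might take the share of clock hours before the injection as a share of events. That needs both an assumed dosing time and an even spread of onsets.
- A reader might add 5 percentage points (1/20) for every pre-injection event. That holds only for a subject not already counted and a denominator of exactly 20.

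**Conclusion.** The asymmetry is real and follows from SAP 9.3 and 9.4.1 read together. A timed pre-injection event is dropped on Day 1 and counted at Visit 2, and no other section removes it. Measured against the Day 1 rule, the effect on the Visit 2 count is upward or nil. Missing start times work in the same direction.

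Its size cannot be fixed from the documents. Under the assumed 1% to 5% chance per subject, it amounts to 0.2 to 1.0 expected subjects out of 20. The direction of the percentage is also open, because subjects never given a second dose would lower it if the Safety Set is the denominator. That offset would be a second distortion, not a remedy. This is a stated rule giving an inconsistent result in the display meant to screen for infusion reactions. It is worth correcting before database lock, but it is not evidence that second-dose reactions will be overstated.

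**What to change.** For SAP 9.4.1, Tables 14.3.2.1 and 14.3.2.2 and Listing 16.2.7.2:
- At each dosing visit, include adverse events that start on the dosing date unless they are recorded as starting before that visit's own administration start time.
- State in SAP 9.3 that an untimed event on the treatment start date counts as treatment-emergent. Without this, keeping untimed events would still favour Visit 2, because an untimed Day 1 event meets no timing clause.
- Show timed pre-administration events at either visit on a separate line. On Day 1 these are not treatment-emergent and should be labelled so, because Protocol 9.5.4 confines its summaries to treatment-emergent events.
- Use the number of subjects dosed at that visit as the denominator.

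The cost is a few sentences in two SAP sections and a small programming change. Protocol 6.4 and SAP 9.2 already require the date and time of each dose, and SAP 9.3 presupposes event start times, so no new data should be needed. The change to SAP 9.3 would also bring any untimed Day 1 events into the other treatment-emergent tables, and the SAP should say so. No clinical procedure changes.

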6.4 Study Intervention Compliance

Only subjects enrolled in this study may receive treatment with ¹²⁴I-AT-01. All study drug during the study will be administered by qualified clinical site staff. The date and time for each dose will be recorded in the CRFs. The date of and reason for any deviations in protocol-specified dosing will be documented in the case report forms.

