7.1.1 Specific Stopping Criteria

7.1.1.1 Infusion-related Reactions

Infusion-related reactions (IRRs) can be any signs or symptoms experienced by subjects during the infusion of pharmacologic or biologic agents or any event occurring on the first day of the infusion (Doessegger 2015). IRRs have been reported, among other terms, as anaphylaxis, anaphylactoid reactions, cytokine release syndrome, hypersensitivity reaction, etc. Symptoms suggestive of an IRR include but not limited to the following: tachypnea with respiratory distress, new onset rash or pruritus, chills, stridor, wheezing, swollen or itchy lips or tongue, onset of abdominal cramping, or hypotension.

Treatment-emergent adverse events starting on the day of ¹²⁴I-AT-01 administration will be summarized to evaluate potential infusion-related reactions.

Subjects will be monitored for IRRs and managed as follows:

- During administration of ¹²⁴I-AT-01: if an IRR occurs during administration, the administration will be immediately discontinued and the subject will be treated for their symptoms and discontinued from the study. Activities for Safety Follow-up 1 (1-3 days after the second administration) and Safety Follow-up 2/EOS (28 (± 3) days after the second administration) will be conducted, per the SoA (Section 1.3).
- After administration of ¹²⁴I-AT-01: if an IRR occurs in a subject after completion of the administration, the subject will be treated for their symptoms, managed in accordance with standard of care, and the IRR will be recorded as an AE. If the symptoms respond promptly to minimal intervention (e.g., responds promptly to symptomatic treatment with antihistamines, acetaminophen, or nonsteroidal anti-inflammatory drugs (NSAIDs)) then, at the discretion of the Investigator, the subject may continue in the study. If the symptoms are prolonged (e.g., not rapidly responsive to symptomatic medication), require IV fluids or treatments, or require hospitalization, the subject will be discontinued from the study. Activities for Safety Follow-up 1 (1-3 days after the second administration) and Safety Follow-up 2/EOS (28 (± 3) days after the second administration) will be conducted, per the SoA (Section 1.3).

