2 PURPOSE OF THE ANALYSES

The purpose of this statistical analysis plan (SAP) is to provide detailed information to aid in the implementation of the statistical analysis of the study data. It briefly summarizes the protocol, describes the analysis sets that will be analyzed, and describes the analyses to be performed. The details of the specific statistical methods that will be used are provided. Table, figure, and listing specifications are in separate documents. This analysis plan is meant to supplement the study protocol. If differences occur between analyses described in the SAP and the current protocol, those found in this SAP will assume primacy.

This SAP is written with due consideration of the recommendations outlined in the most recent International Conference on Harmonisation (ICH) E9 Guideline entitled Guidance for Industry: Statistical Principles for Clinical Trials and the most recent ICH E3 Guideline, entitled Guidance for Industry: Structure and Content of Clinical Study Reports and will be finalized prior to database lock.

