9.2 Extent of Exposure

Only subjects enrolled in this study may be treated with ¹²⁴I-AT-01. During the study, qualified clinical site staff will administer all study drug. The date and time for each dose will be recorded in the CRFs.

The actual dose of ¹²⁴I-AT-01 will be summarized in mCi and mg by study visit. The administration type (infusion, IV bolus), duration of administration (for infusions) and number of subjects experiencing an administration interruption and associated reason for interruption will be summarized by study visit.

 124 AT-01 compliance is defined as receiving 1 mCi (+/- 10%) (<= 2mg 124 AT-01). KI compliance is defined as receiving KI orally for 3 days in the specified time periods. The number of and percent of compliant subjects for 124 AT-01 and for KI will be summarized by visit.

A listing of all administrations of ¹²⁴I-AT-01 will be provided by subject and visit.

A listing of all administrations of potassium iodide (KI) will be provided by subject and visit.

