16.2.4.6	Pregnancy Test Results	Safety
16.2.5.1	¹²⁴ I-AT-01 Administration	Safety
16.2.5.2	Potassium Iodide Administration	Safety
16.2.6	Imaging Results	Image Evaluable
16.2.7.1	Adverse Events by Subject, System Organ Class, and Preferred Term	Safety
16.2.7.2	Treatment-Emergent Adverse Events on Day of Dosing by Subject, System Organ Class, and Preferred Term	Safety
16.2.7.3	Treatment-Emergent Adverse Events on Day of Dosing Reported on the AT01 Administration CRF	Safety
16.2.8.1	Laboratory: Chemistry	Safety
16.2.8.2	Laboratory: Hematology	Safety

Page **37** of **38**

Version Date: 2022-12-16 Version: 2.0

Document Control No.: TMP-SA-008-01 Template Effective Date: 23 Mar 2021

Attralus, Inc.

 $Statistical\ Analysis\ Plan-AT01-001$

16.2.8.3	Laboratory: Urine and Biomarker Results	Safety
16.2.8.4	Vital Signs	Safety

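### SAP 9.4.1 would list any stopped or interrupted administration as an infusion-related reaction, whatever reason was recorded (minor; one listing affected)

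*SAP*

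**What the plan says.** SAP 9.4.1 opens by describing IRRs as "any signs or symptoms experienced by subjects during the infusion of pharmacologic or biologic agents or any event occurring on the first day" when the agent is given. It then plans a summary, by system organ class and preferred term, of treatment-emergent adverse events (TEAEs) that start on a dosing day, and a listing of those events. Its last sentence adds a second route: "IRRs which occur during administration will be captured on the AT01 Infusion CRF as any non-blank answer for" either of two free-standing fields, one for the reason for discontinuation and one for the reason for interruption. The records found this way go into a listing.

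The only listing in SAP 15.1 that fits is 16.2.7.3, titled "Treatment-Emergent Adverse Events on Day of Dosing Reported on the AT01 Administration CRF". The match is inferred from the title, because 9.4.1 speaks of an infusion CRF and the title of an administration CRF. SAP 2 notes that "Table, figure, and listing specifications are in separate documents".

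Three other places bear on the rule:
- Protocol 6.4: "The date of and reason for any deviations in protocol-specified dosing will be documented in the case report forms".
- Protocol 7.1.1.1: "if an IRR occurs during administration, the administration will be immediately discontinued", and the subject leaves the study.
- SAP 9.2, under exposure: the "number of subjects experiencing an administration interruption and associated reason for interruption will be summarized by study visit".

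**The concern.** The two fields ask why an administration stopped or paused. The rule turns any reply into an IRR, with no condition on its content, no tie to an adverse event record and no medical review. A line fault or a dose-preparation problem is not a sign or symptom, and it is not an adverse event under Protocol 10.3.1, which requires an untoward medical occurrence. Under the rule it would be listed as an IRR, and under the apparent listing title also as a TEAE.

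IRR is the first product risk in Protocol Table 1, and the safety of repeat dosing is the secondary objective. A listing meant to show reactions during administration should not mix them with technical stops.

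**Working it through.** The plan gives no figure for this point. The check is a comparison of texts, followed by bounds on the size.

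**1. Rule against definition.** The definition in 9.4.1 looks at what happened to the subject. The rule in the same section looks only at whether a reason field is filled. The two agree only if every recorded reason is a reaction.

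**2. Can another reason be recorded?** Protocol 6.4 has the CRFs hold the reason for any dosing deviation, not only reactions. SAP 9.2 summarises interruption reasons as exposure data, which suggests that they vary. Neither text names the content of these two fields, so together they make non-reaction entries likely to be possible but do not prove it.

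**3. What Protocol 7.1.1.1 implies.** If it is followed, an IRR during administration ends the administration. The cases are then:
- discontinued for a reaction: listed as an IRR, correctly;
- discontinued for another reason: listed as an IRR, wrongly;
- interrupted and resumed for another reason: listed as an IRR, wrongly;
- interrupted and resumed for a reaction: should not occur.

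So, for resumed administrations, the interruption field picks up only non-reactions when the protocol is followed.

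**4. Is it a worst-case rule for missing data?** No. SAP 9.3.2 has such rules, for example "Records with missing CTCAE grade will be counted as severe". They apply when a value is absent. Here the reason is recorded and the rule ignores it.

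**5. Reach.** The day-of-dosing TEAE tables (14.3.2.1, 14.3.2.2) and the hypersensitivity table (14.3.2.4) are built from adverse event records and do not use the rule. No IRR rate is computed from it.

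**6. Bounds on size.**
- Planned administrations: up to 20 subjects x 2 doses = 40, before replacements.
- Volume of an undiluted dose, from Protocol Table 2 (1 mCi at 0.1 to 1 mCi/mL): 1 / 1 = 1 mL to 1 / 0.1 = 10 mL.
- Bolus time at 1 mL per 5 seconds: 1 x 5 = 5 s to 10 x 5 = 50 s. An infusion takes 2 to 5 minutes.
- Frequency of non-reaction stops: not given, and none is assumed here. Such short administrations leave little time for one.

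**The case against.** The strongest reply is that this is a supplementary listing and not the IRR analysis. That analysis is the adverse-event-based day-of-dosing summary, with the hypersensitivity table beside it. This stands, and it is why the point is minor.

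Read generously, the sentence says where reactions will be found, not that every entry is one. As a screen it errs towards inclusion: a reaction entered in either field cannot be lost, and a mild symptom met with a pause, against the protocol, would still be caught. Listing every stop among some 40 administrations is reasonable. This stands as a reason to keep every stop in the listing. It does not justify labelling every stop as an IRR, which is what the sentence does when used as a selection rule.

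The CRF and the listing specifications are not available. The response options might be limited to reactions, or the programmed listing might be limited to TEAEs as its title suggests. Neither can be excluded, but the SAP text states no such limit.

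SAP 9.2 already shows interruptions with their reasons, so a technical pause can be recognised there. This stands for interruptions. Section 9.2 promises no such summary of reasons for discontinuations.

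A reader might infer from the cases above that two in three listed IRRs would be false, or that the reported IRR incidence would be inflated. The documents support neither. The cases are logical combinations, not events with frequencies, and no incidence is derived from these fields.

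**Conclusion.** The rule is wrong as written, and the matter is minor. A discontinuation or interruption for a non-reaction reason would be listed as an IRR, in conflict with the definition in the same section and, for resumed administrations, with Protocol 7.1.1.1. Each such administration would add one misclassified entry to one listing. The number is unknown and may be zero. No table, percentage or endpoint changes.

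This rests on three assumptions: the fields accept reasons other than reactions, the listing is programmed as 9.4.1 describes, and it is the one numbered 16.2.7.3. If the listing prints the recorded reason, a reader could spot a mislabelled row, but the SAP does not say that it will.

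**What to change.** In SAP 9.4.1, replace the last sentence with a plan to list every discontinued or interrupted administration with its verbatim recorded reason. Flag as an IRR during administration only those whose reason is a sign, symptom or other adverse event. A same-day adverse event alone should not trigger the flag, because an unrelated event hours later, or one due to potassium iodide, could then turn a technical stop into a reaction.

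Before database lock, query any flagged record that has no adverse event record, so that true reactions reach the day-of-dosing TEAE tables. Title the listing as administration discontinuations and interruptions, not as TEAEs.

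The cost is a sentence or two in 9.4.1, one listing title, and a short review of what should be few recorded reasons. No new data are needed.
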